### PLANNED ENROLLMENT REPORT

| DOMESTIC PLANNED ENROLLMENT REPORT (SCREENING)  |                        |           |                    |          |           |  |
|---|------------------------|-----------|--------------------|----------|-----------|--|
| Racial Categories                               | Ethnic Categories      |           |                    |          | Total     |  |
|   | Not Hispanic or Latino |           | Hispanic or Latino |          |           |  |
|   | Female                 | Male      | Female             | Male     |           |  |
| American Indian/
Alaska Native               | 1                      | 1         | 0                  | 0        | 2         |  |
| Asian   | 2                      | 2         | 0                  | 0        | 4         |  |
| Native Hawaiian or
Other Pacific
Islander | 1                      | 1         | 0                  | 0        | 2         |  |
| Black or African
American                    | 4                      | 4         | 0                  | 0        | 8         |  |
| White   | 23                     | 23        | 3                  | 3        | 52        |  |
| More Than One
Race                           | 2                      | 2         | 1                  | 1        | 6         |  |
| Total                                    | 33              | 33 | 4           | 4 | 74 |  |

| DOMESTIC PLANNED ENROLLMENT REPORT (TREATMENT)  |                        |           |                    |          |           |  |
|---|------------------------|-----------|--------------------|----------|-----------|--|
| Racial Categories                               | Ethnic Categories      |           |                    |          | Total     |  |
|   | Not Hispanic or Latino |           | Hispanic or Latino |          |           |  |
|   | Female                 | Male      | Female             | Male     |           |  |
| American Indian/
Alaska Native               | 1                      | 1         | 0                  | 0        | 2         |  |
| Asian   | 2                      | 2         | 0                  | 0        | 4         |  |
| Native Hawaiian or
Other Pacific
Islander | 1                      | 1         | 0                  | 0        | 2         |  |
| Black or African
American                    | 4                      | 4         | 0                  | 0        | 8         |  |
| White   | 20                     | 20        | 1                  | 1        | 42        |  |
| More Than One
Race                           | 2                      | 2         | 1                  | 1        | 6         |  |
| Total                                    | 30              | 30 | 2           | 2 | 64 |  |

### 9.3 Stratification Factors

#### Site of disease (1 level of stratification with 3 categories):

After the screening phase, eligible subjects will undergo stratified randomization according to the site of disease: 1) gallbladder cancer (GBC); 2) intrahepatic (IHC); and 3) extrahepatic cholangiocarcinoma (EHC) to ensure similar distribution of BTCs subtypes across treatment arms. There will be no further stratification based on other patient or tumor characteristics (such as age, sex) in this trial. Sample size calculations were performed without stratification, as the sample size is small.

### 9.4 Analysis of Secondary Endpoints

#### Clinical Secondary Endpoints:

##### Overall survival (OS)

OS is defined as the duration of time from start of study treatment to time of death. For subjects lost to follow-up or whose vital status is unknown, every effort will be made to determine the date such subjects were last known to be alive. Such efforts may include phone calls, certified mail, and the checking of public records. Subjects who are alive or lost to follow-up as of the data analysis cutoff date will be right-censored. The censoring date will be determined from the date the subject was last known to be alive. OS will be summarized descriptively using the Kaplan-Meier method. The analysis of OS will be performed on all randomized patients, as well as all the individuals who complete at least one dose of therapy. Median OS will be reported and the associated 95% confidence interval will be estimated.

#### Correlative Secondary Endpoints:

##### Change in T-Cell populations (TILs):

The density of CD8+ T cells in each treatment group, at baseline and after treatment, will be visualized using boxplots, and described using summary statistics including means and standard deviation presented with 95% confidence intervals. A student t-test or nonparametric Wilcoxon rank-sum test will be used to determine whether the increase in CD8+ T cells is greater in treatment arm B (combination atezolizumab and CDX-1127 (varlilumab) plus cobimetinib) than in treatment arm A (atezolizumab and CDX-1127 (varlilumab)).

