## 2.4 Correlative Studies Background

### 2.4.1 CD8+ effector cells

Integrated biomarker assessed with IHC using Cell Marque, CD8 (C8/144B) mouse monoclonal antibody (Ref#108M-98, status IVD, Validated for CTEP by study collaborator [name].

Our primary correlative objective will be to compare infiltration of CD8+ T cells into the tumor microenvironment between patients receiving atezolizumab and varilumab and those receiving this same combination with concurrent cobimetinib. This validated metric will be considered an integrated biomarker for the clinical study.

It has been demonstrated in various malignancies that the presence of CD8+ effector T cells within tumors increases the likelihood of responding to PD-1/PD-L1 antibody blockade (ICB) (Chen *et al.*, 2020; Maibach *et al.*, 2020).

This correlative objective has two distinct hypotheses. First, we hypothesize the combination of atezolizumab and varilumab will increase the total number of CD8+ T effector cells and lead to an increased intratumoral ratio of CD8+ T effector cells CD4+FoxP3+ T regulatory cells. We postulate this effect will be further augmented in patients receiving concurrent cobimetinib. Second, we hypothesize that greater treatment-related changes in CD8+ T cell infiltration will occur in biliary tract tumors and that increased CD8+ T cell infiltration will correlate with a favorable clinical response to therapy.

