### 5.5.2 Fresh Tumor Specimens

- a. Supplies
  - i. 10% Neutral Buffered Formalin (ambient/room temperature) (VWR #16004-115)
  - ii. Cryovial tubes – 1.8 ml cryotubes/vials (e.g., Nunc Code #377267 or equivalent)
  - iii. Conical tubes – 15 mL (e.g., Sarstedt Code #62.554.001 PP or equivalent)
- b. For patients with tumor that is amenable to biopsy, core biopsies will be collected at study baseline and at cycle 1 day 21 (+/-5 days).
- c. A maximum of 5 core biopsies (or fine needle aspirates, if cores are considered unsafe) will be obtained from each subject whose tumor is amenable to undergo a biopsy.
- d. The biopsies will be used to prepare paraffin embedded and frozen samples. A total of 5 biopsies is preferred, when possible.
- e. The first pass will generally be used for on-site examination of the material, to determine presence and quality of lesional tissue.
- f. The remaining biopsy tissue will be paraffin embedded and frozen at each

respective institution.

- g. If a limited amount of tumor tissue is obtained, paraffin embedded tissue should be prioritized over frozen tissue.
- h. Archived or freshly obtained paraffin embedded formalin fixed (FFPE) or frozen tissues of biopsied specimens are needed for the purposes of:
  - i. Pathological examination (for conventional pathology examination, such as H&E stain)
  - ii. Examination of immune and inflammatory fibroblast biomarkers via IHC or IF analysis, as appropriate.
  - iii. Future analysis of genomic and transcriptome features within the tumor microenvironment.
- i. *Samples will be collected in this order:*
  - i. Core 1 – Formalin-fixed paraffin-embedded (FFPE)
  - ii. Core 2 – FFPE
  - iii. Core 3 – Snap Frozen
  - iv. Core 4 – FFPE
  - v. Core 5+ – Snap Frozen
  - vi. *For example, if only 2 cores are obtained, one core should be FFPE and one core should be snap frozen.*
- j. Formalin-Fixed Paraffin-Embedded (FFPE) Tumor Specimens guide
  - i. FFPE tumor tissue block(s) must be submitted. The optimal block is at least 70% tumor.
  - ii. Specimen size requirement is as follows:
    - 1. Surface area: 25 mm^2 is optimal. Minimum is 5 mm^2.
    - 2. Volume: 1 mm^3 optimal. Minimum volume is 0.2 mm^3, however the success of DNA extraction decreases at suboptimal tissue volume.
- k. Snap Frozen Specimens guide
  - i. The biopsy specimen should be placed in a 1.8 ml cryotubes/vials (e.g., Nunc Code #377267 or equivalent)

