## 6. TREATMENT PLAN

### 6.1 Agent Administration

Treatment will be administered on an outpatient basis. For all patients, atezolizumab is administered first, followed by CDX-1127 (varlilumab). For patients on Arm A and on infusion days, cobimetinib is to be taken prior to starting atezolizumab. Reported adverse events and potential risks are described in Section 10. Appropriate dose modifications are described in Section 7. No investigational or commercial agents or therapies other than those described below may be administered with the intent to treat the patient's malignancy.

| Regimen Description -Arm A |   |        |  |               |                   |
|----------------------------|---|--------|--|---------------|-------------------|
| Agent                      | Premedication; Precautions  | Dose   | Route  | Schedule**    | Cycle Length      |
| Atezolizumab               | Premeds are not permitted for the first infusion. If patient experiences an Infusion-Related Reaction (IRR), pre-medication with antihistamines may be administered for subsequent infusions at the discretion of the treating physician. | 840 mg | IV (Initial dose delivered over approximately 60 minutes. Subsequent infusions may be delivered over approximately 30 minutes if initial infusion is tolerated without infusion-associated AEs.) | Days 1 and 15 | 28 days (4 weeks) |
|                            |   |        |  |               |                   |

|   |  |       |    |                  |  |
|---|--|-------|----|------------------|--|
|   |  |       |    |                  |  |
| Cobimetinib   | Cobimetinib should be taken at the same time every morning. It can be taken with or without food*. | 60 mg | PO | Daily, Days 1-21 |  |
| 
* The patient will be requested to maintain a medication diary of each dose of medication. The medication diary will be returned to clinic staff at the end of each course (Appendix E). If patient misses a day, they should resume their normal dose/time the next day and not "make up" the missed dose. If patient is unable to take their dose within 4 hours of regularly scheduled time on the same day, that day's dose should be considered missed and not taken. Resume dosing at the next scheduled dose/time.
  |  |       |    |                  |  |

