## 7.2 Cobimetinib plus Atezolizumab and CDX-1127 (varlilumab) (Treatment Arm A patients only)

### 7.2.1 Recommended Cobimetinib Dose Modifications

In order to standardize the management of AEs, suggested treatment management algorithms for adverse events of particular concern for cobimetinib plus atezolizumab & CDX-1127 (varlilumab) are included in Section 7.3. The following general dose modifications table for cobimetinib is for AEs not specified in the subsequent tables.

| Grade (CTCAE) a  | Recommended Cobimetinib Dose   |
|---|--|
| Grade 1 or Grade 2 (tolerable)  | No dose reduction. Maintain cobimetinib at a dose of 60 mg QD (3 tablets)            |
| Grade 2 (intolerable) or Grade 3 b or 4 (any)
First appearance | Interrupt treatment until Grade $\leq 1$ , restart treatment at 40 mg QD (2 tablets) |
| Second appearance  | Interrupt treatment until Grade $\leq 1$ , restart treatment at 20 mg QD (1 tablet)  |
| Third appearance   | Consider permanent discontinuation   |

CTCAE = Common Terminology Criteria for Adverse Events; NCI = National Cancer Institute; QD = once daily.

a The intensity of clinical adverse events graded by NCI CTCAE v5.0.

b An exception to this is for Grade 3 anemia, without presence of hemorrhage and/or hemolytic process. In this case, participants can be treated with transfusions as needed in order to improve to grade 2 or better and do not require treatment interruption or dose

reduction. If recurrent transfusions are needed, treating provider can consider dose reduction.

Toxicities will be evaluated using NCI CTCAE v5.0. If toxicity occurs, the toxicity will be graded and appropriate supportive care treatment will be administered to decrease symptoms.

Generally, in the case of Grade 4 hematologic or Grade 3 to 4 non-hematologic toxicity (except for Grade 3 skin cancer, squamous or basal cell type), treatment with cobimetinib should be interrupted until recovery to baseline or Grade 1 and then resumed at one dose level reduction. Below is a table for cobimetinib dosing upon dose modification:

| Dose level | Dose                             |
|------------|----------------------------------|
| 0          | 60 mg QD 21 days out of 28 days  |
| (-1)       | 40 mg QD, 21 days out of 28 days |
| (-2)       | 20 mg QD, 21 days out of 28 days |

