|   | H: Clinical hematology: CBC with differential ANC, ALC, AEC, and platelet count. Labs may be collected within a window of up to 7 days prior to Cycle 1 Day 1 dosing and up to 3 days prior to all other dosing days. Initial screening bloodwork does not need to be repeated if performed within 7 days of CD1.  |                     |        |        |         |       |        |                    |        |       |  |
|   | I: Serum Chemistry should include Glucose, Calcium, Sodium, Potassium, $\text{CO}_2$ , Chloride, BUN, Creatinine, Alkaline phosphatase (ALT), Aspartate amino transferase (AST), Bilirubin, Albumin, GGT, Total Protein, and LDH. For patients on Arm A (i.e. receiving cobimetinib), also include Phosphorus and Magnesium. Labs may be collected within a window of up to 7 days prior to Cycle 1 dosing and up to 3 days prior to all other dosing days. Initial screening bloodwork does not need to be repeated if performed within 7 days of CD1.  |                     |        |        |         |       |        |                    |        |       |  |
|   | J: Baseline thyroid testing should be done only in patients with a known history of thyroid dysfunction and/or if there is a clinical concern for thyroid dysfunction at the time of study screening. Free T3/T4 should be checked reflexively if fTSH is abnormal. Subsequent labs during treatment may be collected within a window of up to 3 days prior to dosing days.  |                     |        |        |         |       |        |                    |        |       |  |
|   | K: Serum or urine pregnancy (women of childbearing potential only) is required at baseline. For women with a mildly elevated B-HCG who in the opinion of the investigator are not pregnant, a vaginal ultrasound must be obtained to confirm that the participant is not pregnant in order to enroll on this study. Pregnancy tests during treatment as clinically indicated.  |                     |        |        |         |       |        |                    |        |       |  |

| Visit window d  | Baseline                           |                      | Cycle 1 |        |        | Cycle 2 |       |        | Cycle 3 and beyond |        |       | Progression/
End of
Treatment e |        |        |
|--|------------------------------------|----------------------|---------|--------|--------|---------|-------|--------|--------------------|--------|-------|--|--------|--------|

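### Section 9.4 reverses the arm letters in the CD8+ comparison and leaves the test as t-test or rank-sum on the increase; correct the letters and fix one baseline-adjusted analysis

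*Combined protocol and SAP*

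**What the plan says.** Section 9.4, under the correlative secondary endpoints, plans summaries of CD8+ density at baseline and after treatment by arm, then a between-arm comparison: "A student t-test or nonparametric Wilcoxon rank-sum test will be used" to see whether the increase "is greater in treatment arm B (combination atezolizumab and CDX-1127 (varlilumab) plus cobimetinib) than in treatment arm A", which it describes as the doublet.

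Elsewhere the letters run the other way:

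- Section 6.1: "For patients on Arm A and on infusion days, cobimetinib is to be taken prior to starting atezolizumab".
- Heading of Section 7.2: "Cobimetinib plus Atezolizumab and CDX-1127 (varlilumab) (Treatment Arm A patients only".
- Section 11, footnote I: "For patients on Arm A (i.e. receiving cobimetinib), also include Phosphorus and Magnesium". Footnotes D, T, U, V and Z likewise tie cobimetinib, or the monitoring for it, to Arm A.

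Section 2.4.1 sets the aim and direction: "Our primary correlative objective will be to compare infiltration of CD8+ T cells into the tumor microenvironment", with and without cobimetinib, and "We postulate this effect will be further augmented in patients receiving concurrent cobimetinib". Section 5.5.2 limits who contributes tissue: "For patients with tumor that is amenable to biopsy, core biopsies will be collected at study baseline and at cycle 1 day 21".

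**The concern.** There are two separate problems in one sentence of the analysis plan.

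First, the comparison is directional and the letters attached to it are wrong. Code or tables keyed to the letters would test or label it backwards.

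Second, two tests are offered with no rule for choosing between them, and no scale is stated. Both use the baseline density only by subtracting it, although regressing on it needs no further data. Section 2.4.1 treats this as the primary correlative objective, and CD8+ is the only tissue biomarker that Section 5.8 labels integrated. Biopsy depends on accessible tumour, so pairs may be few and precision is worth having.

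**Working it through.** **Letters.** Section 9.4 has B as triplet and A as doublet. Sections 6.1, 7.2 and 11 have A as the arm taking cobimetinib. Section 9.4 stands alone, and its own regimen descriptions agree with the direction in 2.4.1. Only the letters are wrong.

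**Open choice of test.** The plan has no figure to reproduce for this endpoint: no power, SD, correlation, effect size, level or sidedness. If both tests were run and the smaller p-value kept, simulation (20,000 runs, nominal two-sided 0.05, 16 or 32 pairs per arm) gives a type I error of about 0.057 to 0.060 for normal changes and 0.062 to 0.069 for skewed ones.

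**Precision.** All inputs are assumptions. Let *s* be the baseline SD, *ks* the on-treatment SD, *r* their correlation and *n* the pairs per arm.

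- Change score: variance of the arm difference = 2s²(1 + k² − 2rk)/n.
- ANCOVA: 2k²s²(1 − r²)/n, times 1 + 1/(2n − 4) for estimating the slope.
- Large-sample ratio, ANCOVA to change score: k²(1 − r²)/(1 + k² − 2rk).

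For r = 0.3/0.5/0.7:

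- k = 1: 0.91/1.40, 0.75/1.00, 0.51/0.60 = 0.65/0.75/0.85, so the standard error is 19%/13%/8% smaller.
- k = 1.5: 2.0475/2.35, 1.6875/1.75, 1.1475/1.15 = 0.87/0.96/1.00.
- 20 pairs per arm (factor 1 + 1/36 = 1.03): 0.67/0.77/0.87 for k = 1 and 0.90/0.99/1.03 for k = 1.5.
- 10 pairs per arm (factor 1 + 1/16 = 1.06), k = 1.5: simulated 0.92/1.03/1.06, a loss of up to about 6%.

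**Power.** Simulation with 10,000 trials per setting, log-normal densities without zeros, baseline log-SD 1.0, a 2.2-fold effect, two-sided 5% and 20 pairs per arm, for r = 0.3/0.5/0.7:

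| Analysis | k = 1 | k = 1.5 |
|---|---|---|
| Log-scale ANCOVA | 0.72/0.80/0.93 | 0.40/0.46/0.62 |
| Log-change t-test | 0.55/0.69/0.89 | 0.36/0.46/0.63 |
| Raw-change t-test | 0.44/0.54/0.70 | 0.17/0.19/0.23 |
| Raw-change rank-sum | 0.56/0.68/0.87 | 0.32/0.40/0.52 |

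The first two rows isolate adjustment. The distance from the first row to the last two also includes the move to the log scale.

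**Zeros.** Suppose 20% of densities are zero (assumed), with equal SDs, 20 pairs per arm and an offset of 0.01. At r = 0.7, log-ANCOVA has power 0.74, the rank-sum test on the increase 0.86, and a rank-based ANCOVA 0.89. The log version therefore depends on the offset when zeros are common.

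**The case against.** The letter swap is editorial, since the sentence spells out both regimens. That stands. A reader might infer that the trial would test the hypothesis in reverse, but only work keyed to the letters could go wrong.

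A two-arm test of change is valid for a small correlative endpoint, and no document figure shows that ANCOVA will do better. At an SD ratio of 1.5 it gains almost nothing over a log-change t-test, and with zeros the planned rank-sum test can beat log-ANCOVA. That also stands. A reader might take 0.72 against 0.44 in the table as the benefit of adjustment, but much of it comes from the scale. The powers are two-sided, whereas the planned question is directional with no sidedness stated.

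A reader might also infer that the analysis set and baseline are undefined. That goes too far. Section 2.4.3 says paired samples from the baseline and cycle 1 day 21 biopsies will be used, although under an exploratory heading, and Sections 5.1 and 5.2 keep archival tissue apart from baseline. What 9.4 lacks is a cross-reference and a level: missing detail only.

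Finally, patients with pairs are a post-randomisation subset. Biopsy depends on access, and Section 4.3.2 and footnote P of Section 11 place the baseline biopsy after randomisation, in an open-label trial. If a baseline imbalance arose in that subset and would have persisted untreated, ANCOVA would be biased by (1 − slope) times the imbalance, while the change score would not. The remedy does not remove this, so pairs must be reported by arm.

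**Conclusion.** The letters in Section 9.4 are wrong, with high confidence. It is a labelling error in the analysis section, and the intended direction is not in doubt.

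The choice of test is left open and unadjusted. One pre-specified baseline-adjusted analysis would generally be at least as precise. The size of the gain is an assumption throughout: worthwhile if the two SDs are similar, and little, none or slightly negative if the on-treatment SD is much larger and pairs are few. The documents do not support saying that the planned tests are invalid or that ANCOVA always wins.

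Severity is minor. The endpoint is secondary, and no ORR or PFS decision depends on it.

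**What to change.** In Section 9.4:

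1. Swap the letters (Arm A = plus cobimetinib, Arm B = doublet) and define the contrast by regimen, triplet minus doublet.
2. Replace the two-test choice with one pre-specified analysis of cycle 1 day 21 CD8+ density on arm and baseline density. Fix the scale before any CD8+ result is seen by arm: log if zeros are rare, with the offset stated in advance, otherwise a rank-based ANCOVA. Say beforehand what counts as rare. Level and sidedness can go in the same sentence.
3. Keep the rank-sum test on the increase as a sensitivity analysis.
4. Report the number of pairs, and missing pairs with reasons, by arm.

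The cost is a few sentences, with no extra biopsies or data. The statistical price is one degree of freedom, the possible small loss shown above, and, on the log scale, an effect expressed as a ratio rather than an absolute difference.

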##### Pharmacokinetics and Immunogenicity:

- Atezolizumab and CDX-1127 (varlilumab) serum concentrations will be measured using validated ELISAs. Commercially available ELISA assays for atezolizumab will be used to quantify atezolizumab in patient serum samples. For varlilumab, we will develop and validate, per FDA guidance criteria, an ELISA assay using immobilized CD27 and a labeled secondary anti-human IgG1 for detection. Similarly, for immunogenicity, we will establish screening assays for both atezolizumab and CDX-1127 (varlilumab) and perform immunodepletion in bridging assays for samples testing positive for ADAs. This will be completed within the OSUCCC PhASR lab, which is experienced with

bioanalytical assay development and validation per FDA guidance criteria, using ELISA, LC-MS and other platforms.

- Atezolizumab and CDX-1127 (varlilumab) clearance, including a time-varying rate of change, will be determined for each patient using mixed effects pharmacokinetic modeling. The methods for this will include adopting published PK models for atezolizumab as a starting point (e.g. Netterberg, *et al.* 2019; Stroh, *et al.* 2017) and using Bayesian estimation with the published model parameter values as priors in NONMEM (Icon, Dublin, Ireland). As no published mixed effects model for varlilumab is currently available, we will evaluate a basic 2-compartment model as a starting point and add additional structural parameters (e.g. time-varying clearance), as statistically justified. We will use the likelihood ratio test for decision-making when adding each new parameter, using the objective function value (OFV), which is chi-square distributed, and a cut-off of -3.84 change in OFV, which corresponds to a p-value of 0.05 with one degree of freedom. Once a base model is established, we will also evaluate covariates (e.g. albumin, CLcr, ADA, etc.) using forward addition/backward deletion with p = 0.01 as a cut-off for covariate retention.
- The primary assessment will be individual baseline atezolizumab clearance as a continuous variable in uni-variate and multi-variate Cox proportional hazards models for PFS. We hypothesize baseline atezolizumab clearance will be a predictor of PFS (higher baseline atezolizumab clearance will associate with shorter PFS).
- Several secondary assessments will be completed to determine associations of baseline or time-varying atezolizumab clearance with CDX-1127 (varlilumab) baseline clearance, CDX-1127 (varlilumab) time-varying clearance, and presence of cachexia. The secondary assessments will evaluate associations with PFS and OS. We hypothesize patients with high baseline atezolizumab clearance will also have high baseline CDX-1127 (varlilumab) clearance, and that the baseline clearance for both antibodies will be higher in patients with cachexia compared to patients without cachexia.

